13.3. Sample Size Determination

There are 2465 livers in the retrospective control cohort. One-year functional utilisation in this group was calculated using complete organ utilisation data and a Kaplan-Meier estimate of transplant survival at one year, due to a small proportion of censored data prior to that point. One year functional utilisation in the control cohort was 21.8%. A 50% improvement in functional utilisation (to 32.7%) would represent an increase of around 135 extra transplants functioning at 1 year each year in the UK. This would transform waiting list mortality (50 patients in 2019-20) and average waiting times.

There will be some circumstances where, typically due to logistics (e.g. temporary NMP unavailability), centres will preserve a liver in the NMP study cohort using SCS. In the European Phase-3 trial, only one liver randomised to NMP crossed-over to the SCS arm (14). This figure is likely to be higher in the current study due to earlier study entry and logistical constraints, so we have allowed for a 15% crossover rate (25% due to logistical reasons, 5% eligibility message not relayed and 5% general cross-over). We will analyse the data on a modified ITT basis, whereby livers unable to be perfused for logistic reasons are excluded, along with those who were found to be ineligible after study entry.

Allowing for these exclusions and cross-over rate, the sample size was calculated based on an anticipated increase in the primary endpoint from 21.8% in the RWC cohort to 31.4% in the NMP mITT analysis. A 'superiority by a margin' design was used, such that with a 2.5% one-sided significance level the sample size will have 90% power to detect whether NMP is superior to SCS by the prespecified threshold (margin) of 40 extra livers transplanted with one year function per year. As there are 2465 livers in the control cohort, an allocation ratio of 3.5:1 was used to achieve the necessary power and this requires a sample size of 700 liver offers in the NMP study arm. As the primary endpoint uses mandatory data collected by NHSBT, loss to follow-up should be low. Allowing a 25% loss due to exclusions due to being unable to use NMP for logistical reasons and another 10% loss (due to withdrawal of consent, loss to follow-up and those meeting exclusion criteria after study entry), the number required increases to 1035 offers.

Currently, around 1242 eligible livers (i.e. DUI>0.27 and Hep C/HIV negative) are offered each year on average in the UK. Recruitment would therefore require 56% of all eligible livers offered during the 18-month recruitment period to be enrolled in the trial.

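### Section 13.3 gives a 15% crossover rate whose listed parts add to 35%, and the 31.4% planning rate follows from neither figure

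*Protocol*

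**What the plan says.** Protocol section 13.3 gives a control rate of 21.8% and describes a 50% relative improvement, to 32.7%, as the gain that would transform waiting-list mortality. It then allows for a "15% crossover rate (25% due to logistical reasons, 5% eligibility message not relayed and 5% general cross-over". The next sentence but one in substance is the analysis rule: livers that cannot be perfused for logistic reasons are left out of the mITT analysis. Section 13.4 repeats that exclusion, and section 9.4 applies it under the heading of crossovers.

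Allowing for the exclusions and the crossover, the sample size is based on a rise "from 21.8% in the RWC cohort to 31.4% in the NMP mITT analysis". The comparison is against a "prespecified threshold (margin) of 40 extra livers transplanted with one year function per year", which section 13.2 equates to an odds ratio of 1.20. The protocol states that "with a 2.5% one-sided significance level the sample size will have 90% power", with 2465 controls, an allocation ratio of 3.5:1 and 700 offers in the study arm. A 25% loss for logistics and a further 10% loss are then applied, so that "the number required increases to 1035 offers".

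**The concern.** The total and its parts cannot both be right: 25% + 5% + 5% is 35%, not 15%. The paragraph presents 31.4% as the result of these allowances, so the mismatch bears on the effect size that the power calculation uses.

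The 25% also appears in two roles. As an item in the crossover list, it would describe livers that stay in the analysis and dilute the effect. As an mITT exclusion and a loss in the inflation, it describes livers that leave the analysis. A reader cannot tell from the text what dilution was assumed.

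At stake is whether the stated 90% power rests on a planning rate that anyone can reconstruct. Anyone who later compares observed with planned crossover will find 15%, 35% or an implied 12%, with nothing to choose between them.

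**Working it through.** **Inputs, all from Protocol section 13.3 unless noted.** Control rate 21.8%; improved rate 32.7%; planning rate 31.4%; one-sided 2.5% level; 90% power; 2465 controls; 700 study offers; ratio 3.5:1; 1242 eligible offers a year; margin of 40 livers a year (odds ratio 1.20 in section 13.2).

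**Margin.** 40/1242 = 3.22 percentage points. An odds ratio of 1.20 on 21.8% gives 25.07%, or 3.27 points. The two agree closely.

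**Step 1: reproduce the plan from 31.4%.** With unpooled variance and the 3.22-point margin:

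- Study-arm size = [0.314×0.686 + (0.218×0.782)/3.5] × (1.960 + 1.282)² / (0.096 − 0.0322)² = 682. With the 3.27-point margin it is 692, and on the log-odds-ratio scale 676. The plan says 700.
- Power with 700 against 2465: the standard error is √(0.314×0.686/700 + 0.218×0.782/2465) = 0.0194. Then Φ[(0.096 − 0.0322)/0.0194 − 1.960] = 0.908. The range over the three methods is 90.4% to 91.0%.
- Inflation: 700/(0.75×0.90) = 1037, against 1035. Conversely, 1035×0.75×0.90 = 698.6 analysable offers.

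Everything after 31.4% therefore reproduces within rounding.

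**Step 2: try to reproduce 31.4% itself.** Two assumptions are needed: that 32.7% is the undiluted rate, and that crossovers have the control rate. With crossover fraction x in the analysed set, the expected rate is 32.7% − x × (32.7% − 21.8%) = 32.7% − 10.9x%.

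- Solving for 31.4%: x = 1.3/10.9 = 11.9% (11.5% to 12.4% allowing for rounding of 31.4%).
- x = 15%: 31.1%.
- x = 35%: 28.9%.
- Diluting on the log-odds scale gives 30.9% at 15% and 28.6% at 35%.

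Neither printed figure leads to 31.4%.

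**Step 3: readings consistent with the mITT rule.** If the 25% is an exclusion, only the two 5% items remain as crossover. The protocol does not say what they are percentages of.

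| Crossover in the mITT set | Expected rate | Power, 700 v 2465 | Study offers for 90% power |
|---|---|---|---|
| 10% (5% + 5% of the mITT set) | 31.6% | 92.0-92.7% | 629-651 |
| 11.9% (implied by 31.4%) | 31.4% | 90.4-91.0% | 676-692 |
| 10/75 = 13.3% (5% + 5% of all offers) | 31.2% (31.25% unrounded) | 89.0-89.7% | 709-731 |
| 15% (as stated) | 31.1% | 87.2-87.9% | 752-784 |

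The ranges cover both margins and the log-odds-ratio test.

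**The case against.** The strongest reply is that this is a labelling slip with little effect. Section 9.4 uses crossover for any switch to cold storage and then removes the logistic cases, and section 13.3 can be read the same way. The calculation plainly did not dilute by 25%, or the planning rate would be far below 31.4%. The protocol never says that 31.4% was obtained from 32.7%, so the dilution check rests on an assumption. The decision rule is untouched. Planned recruitment ended in October 2023 and the latest version listed in the amendment history is dated July 2024, so a correction changes the record and not the conduct.

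Most of this stands, and it limits the size of the point. It does not remove the wrong total or supply a derivation of 31.4%. The 32.7% is the only full-effect rate in the protocol and is the natural starting point, but it remains an assumption.

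Three stronger readings are tempting, and the protocol does not support them:

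- A reader might infer that true crossover is 35%, with an expected rate of 28.9% and power of only about 52-53% at 700 offers. That would keep the logistic cases in the analysis, and sections 9.4, 13.3 and 13.4 exclude them.
- A reader might add the two losses, giving 700/0.65 = 1077 offers needed, or 1035×0.65 = 673 analysable. The printed 1035 fits the multiplicative calculation (1037), so this is not a live alternative.
- A reader might infer that the logistics share was raised from 15% to 25% without updating the planning rate, because 10/85 = 11.8% leads back to 31.4%. That is a back-calculation. The amendment history records an increased sample size but not which assumption changed.

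**Conclusion.** The point holds as an error in the stated basis of the sample size. The 15% does not equal its parts, the logistics share is named as crossover although it is excluded from the analysis, and the 31.4% follows from neither 15% nor 35%. The mismatch of 15 and 35 is certain. The statement about 31.4% depends on taking 32.7% as the undiluted rate and giving crossovers the control rate.

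The size is modest. Across crossover rates of 10% to 15% in the mITT set, the planning rate runs from 31.6% to 31.1% and power from about 92-93% down to 87-88%. The stated 90% lies inside that range, so the text does not show that the trial is underpowered. It shows that the power cannot be traced to a stated assumption. The 700 and the 1035 are correct given 31.4%.

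**What to change.** Rewrite the crossover and sample-size paragraphs of section 13.3 so that:

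1. the 25% for logistics appears once, as an mITT exclusion that enters the inflation to 1035;
2. the crossover rate is the sum of the remaining parts, with its denominator given (all offers or the mITT set), and the 15% is removed or reconciled with that sum;
3. the planning rate is derived in the text from the undiluted rate and that crossover rate;
4. power is restated for about 699-700 analysable offers. It is about 89-90% if the two 5% figures are shares of all offers, and about 92-93% if they are shares of the mITT set.

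The sponsor must say which denominator was meant, because the protocol does not settle it. The cost is a reworded passage and possibly a stated power slightly below 90%. Recruitment and the analysis do not change.

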13.4. Analysis Populations

A modified intention-to-treat (mITT) analysis will be performed for the primary outcome. Liver offers will be analysed according to whether part of the study arm or RWC cohort, irrespective of whether NMP was actually used in the study arm. The exceptions to this relate to eligibility factors that are unknown at the time of study entry (recipients <18 years, split liver, multi-organ or non-UK transplants, recipient declined consent to NMP or data collection) and livers in the NMP study arm that are unable to undergo perfusion

Clinical Trial Protocol Template version 14.0

CONFIDENTIAL

due to logistical constraints (e.g. lack of trained staff or device availability) – these livers will be excluded from the mITT population. These exclusions are considered appropriate because enrolment prior to organ offer and establishing availability of NMP is for pragmatic reasons only, and the recipient and transplant exclusions are unaffected by participation in the different cohorts.

Secondary (recipient) outcomes will be analysed using a second modified intention-to-treat analysis. As well as excluding livers described above, this analysis will exclude livers offered but not transplanted for any reason.

In addition, secondary per-protocol analyses will be performed for the primary endpoint.

A propensity-score matched analysis will also be undertaken as a secondary analysis to allow for adjustment for any baseline differences between the two cohorts resulting from the non-randomised design. Due to anticipated cross-over in the trial, this will also be used to provide an unbiased estimate of the treatment effect if all livers retrieved in the study arm had adhered to NMP treatment. Exploratory analyses will be undertaken to assess the effect of a 'device to donor' vs 'back to base' approach to NMP on the primary outcome, along with any effect of the duration of NMP and use of NRP. Sensitivity analyses will also be conducted to investigate the impact of any other donor interventions that form part of other research studies within NHSBT OTDT if such interventions are imbalanced between the two cohorts.

We will also undertake the following pre-specified subgroup analyses (if sufficient data are available):

- DBD vs DCD donors, anticipating NMP to have a greater impact in DCD donors
- Impact of donor utilisation index (DUI), analysed according to the quartiles observed and anticipating NMP to have a greater impact in the lower DUI quartiles.
- Impact of donor risk (DLI), analysed according to the quartiles observed and anticipating NMP to have a greater impact in the lower DLI quartiles.

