The participant will be allowed as much time as possible to consider the information, and the opportunity to question the Investigator or other independent parties to decide whether they will participate in the trial. Written Informed Consent will then be obtained by means of dated signatures of the participant and the person who presented and obtained the Informed Consent. The person who obtained the consent must be suitably qualified and experienced and have been authorised to do so by the Chief or Local Principal Investigator. A copy of the signed Informed Consent will be given to the participant. The original signed form will be placed in the patient notes, and a copy retained at the trial site.

If a patient refuses consent for use of data, the liver will be stored as per usual centre practice and the recipient will not be enrolled in the study. If preservation has commenced, perfusion will continue. The liver will then be transplanted to the patient and the recipient will not be enrolled in the study.

Whether or not a patient agrees to participate in the study does not affect organ offering or the chances of receiving a transplant in any way. Once a liver has been offered to the recipient, this offer will be maintained unless the recipient surgeon feels that the liver is not suitable for transplant or the recipient is not medically fit to undergo the procedure.

In circumstances where there is insufficient time for the recipient to consider participation in the study prior to transplant, consent may be deferred to after the transplant procedure. In these cases, no data will be collected until after informed consent has been provided.

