Obtaining informed consent post-transplant may not be feasible in-person due to PLUS liver transplant recipients being discharged back to their local referring specialists, for example. In this situation, the approach can be made by telephone and the written study information/Informed Consent Form (ICF) will be provided via post or email. In order to allow sufficient time for considering participation in the study, this initial approach will be followed up by a further phone call or clinic visit at which point a consent discussion will take place and consent will be requested. If followed-up by phone call, the patient will be asked to confirm consent by signing the ICF and posting or emailing the signed ICF back to the site team. In cases where email is used, the patient will be requested to scan/photograph and send the signed ICF back by replying to an email sent by the local site team/consenter. Guidance on obtaining remote consent is provided in the PLUS Remote Consent Process Guidance document.

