10. DATA COLLECTION FOR RETROSPECTIVE CONTROL COHORT

10.1. Description of data

Outcome data for the retrospective control cohort will all be collected from the National Transplant Registry in an anonymised fashion. Outcomes will mirror those collected for the prospective study cohort, where possible, to allow direct comparison between cohorts. The data fields of the National Transplant Registry that are accessed for the purpose of this study are detailed in the PLUS Data Sources document. Registry data are collected at the time of registration, transplant, month 3 and month 12 post-transplant. Donor data are also available from the registry. These data will be used as the basis for the following assessments.

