13.6. The Level of Statistical Significance

Clinical Trial Protocol Template version 14.0

CONFIDENTIAL

© Copyright: The University of Oxford and Oxford University Hospitals NHS Foundation Trust 2018

The level of statistical significance will be set at a one-sided level of 2.5% for the primary outcome as superiority of NMP is required. For all other hypothesis tests a two-sided significance level of 5% will be used.

13.7. Procedure for Accounting for Missing, Unused, and Spurious Data.

Withdrawals from the trial after implantation will be documented, and a narrative analysis of withdrawals will be performed. Recipients withdrawing from the trial after implantation will be included in analysis using imputation methods for missing data, as described in the SAP.

The primary outcome will be available for all unused livers, and the majority of transplanted livers where the recipient attends a follow-up visit >10 months post-transplant or the liver fails at any point. It is anticipated very few patients will be lost to follow-up, but it is likely that not all measurements at all time points will be recorded for every recipient. Where data are missing from the registry for the study cohort at 3 and 12 months, attempts will be made to chase missing data.

Assuming that registry data are missing at random, with no effect of cohort on the probability of missing data, multiple imputation methods will be used to estimate missing variables. Sensitivity analyses will assess the effect of these assumptions.

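### Excluding study livers for refused data consent removes only transplanted study livers, so it biases functional utilisation downward, and Section 13.4's justification does not hold for consent

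*Protocol*

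**What the plan says.** **The exclusion.** Protocol Section 13.4 lists eligibility factors unknown at study entry that take a liver out of the primary analysis set. One is that the "recipient declined consent to NMP or data collection". Section 7 says the same of recipients who do not consent to use of their data. Section 13.4 defends the recipient and transplant exclusions on the ground that being in one cohort or the other does not affect them.

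**Unused livers.** Section 13.7 states that the primary outcome is available for every unused liver, so each stays in as a failure.

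**Controls.** Section 10.1: "Outcome data for the retrospective control cohort will all be collected from the National Transplant Registry in an anonymised fashion". No consent step applies. Section 8.2 nevertheless describes the criteria as identical in the two cohorts, while Section 8.3 makes informed consent an inclusion criterion.

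**Timing of consent.** Section 9.5.1 seeks consent on admission. Where time is too short, consent may follow the transplant: "In these cases, no data will be collected until after informed consent has been provided". Remote consent is allowed, for example because of "PLUS liver transplant recipients being discharged back to their local referring specialists".

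**Sample size.** Section 13.3 allows a 10% loss that includes withdrawal of consent and treats it as a loss of numbers only. It adds: "As the primary endpoint uses mandatory data collected by NHSBT, loss to follow-up should be low".

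**The concern.** The primary outcome is a proportion of offers: successes over all livers kept in the set. Most transplanted livers are successes, and every unused liver is a failure. An exclusion that reaches only transplanted livers takes out mostly numerator events and leaves the failures untouched. The study rate falls even when refusal has nothing to do with outcome. The control rate cannot move in the same way, so the comparison is no longer like for like, and a threshold-crossing design depends on exactly that.

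At stake are a study effect that reads too small and a lower chance of crossing the threshold when NMP truly works. There is also a second, separate gap. The protocol does not say what happens to a recipient who dies before a deferred consent approach. If such recipients were left out, graft and patient survival would read too high, and those results support the claim that outcome is not compromised.

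**Working it through.** **Inputs from the protocol**
- Test level (13.6): "The level of statistical significance will be set at a one-sided level of 2.5% for the primary outcome".
- Power (13.3): "the sample size will have 90% power to detect whether NMP is superior to SCS" by the margin.
- Rates (13.3): "from 21.8% in the RWC cohort to 31.4% in the NMP mITT analysis".
- Margin: 40 livers per year, OR 1.20 (13.2), on about 1242 eligible offers a year (13.3).
- Size: 700 evaluable study offers against 2465 controls; 1035 enrolled after losses of 25% and 10% (13.3).

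**Assumed inputs**
- Refusal r = 5% to 10% of recipients, unrelated to outcome. The protocol gives no rate.
- 12-month graft survival s = 84% to 90%. The lower value is 0.218/0.26 = 0.84, using the 26% utilisation in Section 5.2, which covers a different period from the control cohort.

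**Step 1: reproduce the plan.**
- Margin: 40/1242 = 3.2 points. On 21.8% this gives 25.0%, OR 1.197, matching 1.20.
- Study-arm n = (1.960 + 1.282)² × (0.314×0.686 + 0.218×0.782/3.5) / (0.096 − 0.0322)² = 682, within 3% of 700.
- Power at 700 v 2465 on the log-OR scale: log OR 0.496, SE 0.0949, (0.496 − 0.182)/0.0949 − 1.96 = 1.34, so power is 0.91.
- Inflation: 700/(0.75×0.90) = 1037, against 1035 stated.

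The sample-size arithmetic is sound.

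**Step 2: apply refusal.** Let p be the true study rate and T = p/s the share of offers transplanted. Removing a fraction r of transplanted livers only gives:
- n′ = 700(1 − rT)
- p′ = p(1 − r)/(1 − rT)

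Worked case, s = 0.84, r = 10%: T = 0.314/0.84 = 0.374. n′ = 700×0.9626 = 674. p′ = 0.2826/0.9626 = 29.4%. OR = 1.49, log OR 0.399, SE 0.0977, (0.399 − 0.182)/0.0977 − 1.96 = 0.26, so power is 0.60.

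| Refusal | s | Observed rate | Power against OR 1.20 |
|---|---|---|---|
| 0% | any | 31.4% | 0.91 |
| 5% | 0.84 | 30.4% | 0.79 |
| 5% | 0.90 | 30.4% | 0.79 |
| 10% | 0.84 | 29.4% | 0.60 |
| 10% | 0.90 | 29.3% | 0.59 |

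With no true effect (21.8% in both cohorts), r = 10% and s = 0.84 give 0.218×0.90/(1 − 0.10×0.218/0.84) = 20.1%, an OR of 0.90.

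**Step 3: why inflation does not help.** Section 13.3 spreads its 10% evenly over offers (1035×0.75×0.90 = 699) and keeps 31.4%. A loss confined to the roughly 37% of offers that are transplanted changes the rate as well as n.

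**Step 4: if recipients who died before approach were dropped.** This is a hypothetical, because the protocol states no rule. Assume 88.0% graft survival and that a fraction e = 2% to 4% of recipients are lost this way.
- Survival reads 0.88/(1 − e) = 89.8% to 91.7%.
- The primary rate reads 0.314/(1 − e×0.314/0.88) = 31.6% to 31.9%.
- With the true rate at the threshold (25%) and s = 0.84, losing 10%, 25% or 50% of all first-year failures raises the chance of a false success from 0.023 to 0.027, 0.033 or 0.048.

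**The case against.** **The main bias is conservative.** Refusals pull the study rate down, so they cannot produce a false claim for NMP. That stands, and it limits the severity. The estimate is still wrong, and power is still lost in a one-off national study.

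**31.4% may already allow for it.** Section 13.3 sets that figure after allowing for exclusions and crossover and calls it the rate in the mITT analysis. Its derivation is not shown, so the power losses above may count some exclusions twice. If so, the true rate lies above 31.4% and the estimate is still too low.

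**A reader might infer that deferred consent drops recipients who die or lose the graft first.** The protocol does not support this.
- Section 13.4 excludes a recipient who declined, and a person never asked has not declined. The text is silent on the case.
- Graft loss does not stop a living recipient from consenting.
- Consent on admission is the default, and deferral is for insufficient time.
- Section 9.5.2 provides a consultee or proxy where capacity is lacking, and its Scottish text keeps those who then die.
- Remote consent concerns recipients who survived to discharge, and it helps to retain them.
- At 88% survival, losing 2% to 4% of recipients would mean that 17% to 33% of all first-year failures came before consent, which is a lot for an exceptional route.

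**A reader might also see a contradiction with Section 13.7**, which imputes for withdrawals after implantation. There is none: those people were enrolled, whereas a refuser under Section 9.5.1 never is.

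**Reporting and imputation detail.** Section 13.2 promises a CONSORT diagram with reasons for exclusions, and imputation methods are left to the SAP, which is not available here. Neither repairs the rule or its justification in Section 13.4.

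**Conclusion.** The point holds for refused consent. As written, the primary analysis set loses transplanted study livers and nothing else through data consent, while controls cannot be lost this way. Section 13.4's justification is therefore wrong on this item. The direction is downward, against NMP. The size is about 1 point at 5% refusal and about 2 points at 10%, with power near 0.79 and 0.60. This rests on assumed refusal rates, on refusal unrelated to outcome, on graft survival of 84% to 90%, and on 31.4% being the rate before consent losses.

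The treatment of recipients who die before a deferred approach is undefined, not misdefined. If they were dropped, survival would be flattered and the primary outcome would move little. The two effects oppose each other, but they bear mainly on different endpoints, so one does not safeguard the other. This should be fixed; it does not undermine the design.

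**What to change.** 1. Correct Section 13.4: withdraw the claim that the consent exclusion is unaffected by cohort.
2. Keep every transplanted study liver in the primary denominator as transplanted, and use its registry outcome wherever that is permitted. Section 14.4 already makes the registry the primary source for 12-month outcomes.
3. Where a refusal must be honoured, do not use that recipient's outcome (Sections 7, 9.5.1 and 9.10 rule it out). Impute 12-month function from the cohort's other transplanted livers, and report best- and worst-case bounds. Section 8.1 gives a precedent: 118 machine-perfused control livers were kept and imputed because excluding them would bias the cohort.
4. State that a recipient never approached because of death is not treated as having declined.
5. Report consent losses by transplant status.

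For s = 0.84 and 10% refusal, about 26 of 262 transplanted livers are affected and 197.8 observed successes remain. Imputation gives (197.8 + 26.2×0.84)/700 = 31.4%, with bounds of 197.8/700 = 28.3% and (197.8 + 26.2)/700 = 32.0%.

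The cost is protocol and SAP wording, some imputation in the primary analysis, and confirmation from the ethics committee and the registry data controller that the liver's transplanted status, and the registry outcome where no refusal exists, may be used. No new data collection is needed.
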